13.2 Stratification

As of the November 2018 Amendment (Amendment #6), patients receiving durvalumab (and in the future, other immunotherapy agents) will be eligible for enrollment in the study. Therefore, exposure to immunotherapy agents will be added as an additional stratification factor.

The randomization and the significance tests applied in the analyses will be stratified by chemotherapy regimen (i.e., platinum with etoposide, platinum with taxane, platinum with pemetrexed) and exposure to immunotherapy agents.

13.3 Randomization

Phase II: Patients will be randomized to either the placebo or nintedanib arm in a 1:2 fashion using a stratified permuted block randomization scheme. The randomization lists to be used in this study will be generated by the study biostatistician. Patients will be included in data analyses according to their randomized treatment assignment irrespective of the treatment actually received (intent-to-treat). After randomization, initiation of the study intervention will take place within the timeframe specified in the eligibility period. Patient randomization will be done electronically by the Department of Biostatistics at RPCI.

The activity of the dose escalation patients receiving durvalumab will not hold enrollment for patients not exposed to immunotherapy agents. (i.e. patients can enroll to Phase II ahead of dose

escalation if the choice is not to give durvalumab. If patient is going to receive durvalumab, it is required to go through dose escalation first until MTD is determined).

13.4 Demographics and Baseline Characteristics

Descriptive statistics (as appropriate: n, percent, mean, median, min and max) will be used to summarize, by treatment group, demographic and baseline characteristics.

13.5 Primary Analysis

Consider a placebo controlled, randomized trial in which patients are stratified by chemotherapy regimen (i.e., platinum with etoposide, platinum with taxane, platinum with pemetrexed) and randomized (1:2 ratio) to a treatment group (placebo versus nintedanib). The primary objective of the study is to evaluate the rate of radiation pneumonitis at 6 months after completion of chemoradiation in patients with unresectable Stage II/III/oligometastatic IV NSCLC who completed chemoradiation followed by nintedanib versus placebo. The primary outcome is radiation pneumonitis status (defined as symptomatic CTC Grade 2 or higher radiation pneumonitis at 6 months after completion of chemoradiation), which is treated as a dichotomous variable.

The primary objective will be assessed using the intent-to-treat principle and a one-sided exact test about the CMH COR:

$$H_0: \theta \geq 1$$

$$H_A: \theta < 1$$

Where θ is the COR for the odds of Grade 2 or higher radiation pneumonitis in the nintedanib treated versus placebo treated populations, stratified by chemotherapy regimen (i.e., platinum with etoposide, platinum with taxane, platinum with pemetrexed). A one-sided test is performed as the rate of radiation pneumonitis is expected to decrease in the nintedanib arm over the placebo arm; that is expect to be $\theta < 1$. The critical value and corresponding rejection region for the one-sided test will be obtained using the exact methods available in SAS v9.4 and maintaining a significance level of 0.05 while accounting for the interim analysis. As of the November 2018 Amendment (Amendment #6), the primary analysis will be conducted excluding the maximum of 18 patients in the durvalumab dose escalation. As a sensitivity analysis, the primary analysis will be repeated with the 6 patients treated at the MTD level from the dose-escalation portion.

13.6 Safety Analysis

The frequency of toxicities will be tabulated by grade. All participants who receive any study treatment will be considered evaluable for toxicity.

13.7 Secondary Analyses

The OS and PFS will be reported by study arm using standard Kaplan-Meier methods. Comparisons of OS and PFS between study arms may utilize the two-sided stratified log-rank test. With a sample size of $n = 33$ in the control and $n = 66$ in the treatment group, there is an 80% chance of detecting a hazard ratio of 0.53 or smaller (with two-sided alpha of 0.05). If the

median PFS in the placebo arm is approximately 2 months, then this would be equivalent to detecting an increase in PFS of at least 1.75 months.

The overall and sub-category QOL and symptom scores (ranging from 0 to 68) will be reported by study arm and time using the appropriate descriptive statistics. Changes in the QOL and symptom scores may be compared between study arms using the Wilcoxon rank sum or independent sample t-tests, as appropriate. No adjustments for multiple testing will be made as this is a secondary analysis. With this sample size, there will be an 80% chance of detecting a change of at least 0.5 standard deviations. A 0.5 standard deviations is equivalent to approximately 9.1 points for the overall QOL and symptoms score; therefore, this study should be able to identify clinically relevant changes in QOL (59).

The PFTs will be reported by study arm and time using the appropriate descriptive statistics. Changes in PFTs, relative to baseline, will be evaluated within each study arm using the Wilcoxon signed rank or paired t-tests, as appropriate. Changes in PFTs may be compared between study arms using the Wilcoxon rank sum or independent sample t-tests, as appropriate. No adjustments for multiple testing will be made as this is a secondary analysis. With this sample sizes, we will have an 80% chance of detecting a change of at least 0.5 standard deviations.

The RP scores will be reported by study arm and time using the appropriate descriptive statistics. Changes in RP scores, relative to baseline, will be evaluated within each study arm using the Wilcoxon signed rank or paired t-tests, as appropriate. Changes in RP scores may be compared between study arms using the Wilcoxon rank sum or independent sample t-tests, as appropriate. No adjustments for multiple testing will be made as this is a secondary analysis. With our sample sizes, we will have an 80% chance of detecting a change of at least 0.5 standard deviations.

The complete response and complete/partial response rates will be reported by study arm and chemotherapy regimen using Wilson 95% confidence intervals. The responses rates will be compared between study arms using the CMH exact test.

The tCLN (tethered cationic lipoplex nanoparticle biochip), mCLN (microfluidic cationic lipoplex nanoparticle biochip) and qRT-PCR (real-time quantitative reverse transcription-polymerase chain reaction) measurements for the expression of miR-1, -21, -127 and -155 will be made on sera collected from NSCLC patients with and with no radiation pneumonitis. The miR expressions, vitamin D levels, and mitochondrial DNA levels will be treated as continuous and reported by radiation pneumonitis status (no versus yes) using the mean, median and standard deviation. Comparisons will be made between groups using a two-sided permutation t-test, as there is no a priori notion of which group will have higher expression.

A pilot model, using the 4 miR expression levels as the biomarker, will be built for classification of patients into 1 of 2 patient populations: radiation pneumonitis versus no radiation pneumonitis. Two classification models will be considered. The first model will treat the miR expressions as dichotomous variables, where the Youden's index method will be used to identify an appropriate threshold. The resulting threshold will maximize the correct classification rate a given miR expression alone was used to classify patients. The second model will treat the miR expressions as continuous variables. Both classification models will be constructed in a similar

fashion using multivariate logistic regression, such that the resulting model predicts the probability of radiation pneumonitis. A set of candidate variables will be obtained from miR expressions and relevant patient characteristics (demographic and clinical). Standard variable reduction techniques will be applied if the number of candidate variables grows large. The variables in the final model will be selected from the set of candidate variables, including possible two-way interaction terms, using forward selection (alpha entry = 0.05) followed by backward elimination (alpha exit = 0.05). Models are fit using Firth's penalized function and model assumptions are verified graphically. Standard bootstrap and cross-validation techniques will be used to calibrate model coefficients. Model performance will be evaluated using calibration plots, receiver operating characteristic (ROC) curves, area under the ROC curve (AUC) and a decision curve. In both models the Youden's index method can also be used to determine the optimal threshold probability for classifying patients, from which standard classification measures can be obtained (sensitivity, specificity, positive predictive value and negative predictive values). As an alternative modeling strategy, classification and regression tree (CART) analysis may also be considered to develop a model using only the miR expressions. These analyses will be repeated using vitamin D, cytokine and mitochondrial DNA levels, alone and in combination with miR expression, to develop classification models.

All secondary analyses will be conducted in SAS v9.4 (Cary, NC), except for CART analysis conducted in R v2.12, at a significance level of 0.05.

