1.4.2 NSCLC

In a Phase II trial in NSCLC patients the safety profile of nintedanib observed in Phase I trials could be confirmed. Most commonly reported drug-related AEs were nausea (57.5%), diarrhoea (47.9%), vomiting (42.5%), anorexia (28.8%), abdominal pain (13.7%) and reversible alanine transaminase (13.7%) and aspartate aminotransferase elevations (9.6%) In conclusion, it was generally well tolerated and displayed single agent activity in advanced or recurrent NSCLC patients. Median overall survival (OS) was 21.9 weeks. Eastern Cooperative Oncology Group (ECOG) 0–1 patients (n = 56) had a median progression free survival (PFS) of 11.6 weeks and a median OS of 37.7 weeks. Tumor stabilization was achieved in 46% of patients (ECOG 0–1 patients: 59%), with one confirmed partial response at 250 mg bid (27).

LUME-Lung 1 was an international, randomized, double-blind, Phase III trial assessing the efficacy and safety of docetaxel plus nintedanib as 2nd line therapy for non-small-cell lung cancer (NSCLC). In total, 1314 patients with Stage IIIB/IV or recurrent NSCLC (all histologies) who had progressed after 1st line chemotherapy were randomized in 1:1 fashion to either receive Nintedanib 200 mg BID + Docetaxel (n = 655) or Placebo BID + Docetaxel (n = 659).

LUME-Lung 1 met its primary endpoint by showing a statistically significant improvement of PFS for all patients regardless of histology (median PFS 3.4 versus 2.7 months; HR 0.79, p = 0.0019) for Nintedanib in combination with docetaxel.

A significant improvement in OS was demonstrated in patients with adenocarcinoma (HR 0.83, $p = 0.0359$, median 10.3 to 12.6 months).

Patients with a poor prognosis defined as time since start of 1st line therapy < 9 months also experienced significant OS improvement from the addition of nintedanib to docetaxel (HR 0.75, $p = 0.0073$, median OS 7.9 to 10.9 months).

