6 PARTICIPANT SELECTION

6.1 Inclusion Criteria

- 1 Age 18 years or greater.
- 2 Histologically or cytologically-proven non squamous cell NSCLC. Mixed histology with SCLC component not allowed.
- 3 Patients with Stage II - IV non squamous cell NSCLC who received at least 54 Gy of total planned thoracic radiation dose will be eligible. Patients must have received at least one cycle of chemotherapy concurrently during the course of thoracic radiation. Regimens allowed are platinum combinations with either etoposide or a taxane regardless of histology subtype; platinum with pemetrexed for patients with nonsquamous NSCLC only. Patients with oligometastatic Stage IV cancer are eligible if they have received only one line of systemic therapy for their Stage IV cancer prior to the concurrent chemoradiation phase.
- 4 Patient must have had a CR/PR/SD, 4-6 weeks after completing last fraction of radiation therapy.
- 5 ECOG Performance Score 0 - 2 (**Appendix C**).
- 6 ANC $\geq 1,500/\mu\text{L}$.
- 7 Platelet count $\geq 100,000/\mu\text{L}$.
- 8 Hemoglobin ≥ 9 g/dL.
- 9 Total bilirubin \leq normal or for those with Gilbert's syndrome ≤ 1.5 times upper limit of normal (ULN) OR direct bilirubin normal (per institute standards).
- 10 AST $\leq 1.5 \times$ ULN. ALT and AST $\leq 2.5 \times$ ULN is acceptable if there is liver metastasis.
- 11 Fertile patients must use adequate contraception.

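### The PFS and OS comparison is valid but makes no use of baseline ECOG status or stage; a pre-specified adjusted Cox model would cost little and could recover some power

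*Combined protocol and SAP*

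**What the plan says.** PFS, OS and 1-year PFS are secondary objectives (Section 3.2). Section 13.7 describes the comparison in one permissive sentence: "Comparisons of OS and PFS between study arms may utilize the two-sided stratified log-rank test". It names no strata. Those come from Section 13.2: "The randomization and the significance tests applied in the analyses will be stratified by chemotherapy regimen", together with the amendment under which "exposure to immunotherapy agents will be added as an additional stratification factor". Three regimens by immunotherapy yes or no gives six cells.

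On power, Section 13.7 states that with 33 placebo and 66 nintedanib patients "there is an 80% chance of detecting a hazard ratio of 0.53 or smaller (with two-sided alpha of 0.05"). It translates this, for a 2-month placebo median PFS, into a gain of at least 1.75 months.

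Eligibility is broad on two other characteristics: "ECOG Performance Score 0 - 2" and "Patients with Stage II - IV non squamous cell NSCLC" (Section 6.1). ECOG is a listed baseline evaluation (Section 9.2 and Table 5). Stage is an eligibility item but is not named in the baseline list. Neither factor enters the randomisation or any planned survival analysis.

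Section 1.4.2 reports a Phase II nintedanib trial in NSCLC with median OS of 21.9 weeks overall, while its ECOG 0-1 patients "had a median progression free survival (PFS) of 11.6 weeks and a median OS of 37.7 weeks".

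**The concern.** When a survival comparison leaves out a strong baseline predictor, three things follow.

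- The hazard ratio averaged over that predictor lies closer to 1 than the one within its levels, and the test has less power.
- With arms as small as 33 and 66, the predictor can be unevenly split by chance, and the single reported hazard ratio carries that imbalance.
- If nothing is specified in advance, an adjusted analysis prompted by a visible imbalance would be data-driven.

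For ECOG the ingredients are all present: a range of 0 to 2, a value recorded before treatment, and evidence in the plan's own background that it separates OS. Stage has a similarly wide range, though the documents give no figure for its prognostic effect.

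**Working it through.** **1. The plan's own figure.** Inputs from Section 13.7: HR 0.53, 33 v 66, two-sided alpha 0.05, power 80%. By Schoenfeld's formula, events = (1.960 + 0.842)² / [(1/3)(2/3)(ln 0.53)²] = 7.85 / (0.2222 × 0.4031) = 87.6, so 88. The plan states no event count. With exponential PFS (placebo median 2 months) and 12 months of follow-up, expected events are 33(1 − 0.0156) + 66(1 − 0.1103) = 32.5 + 58.7 = 91.2, giving about 81.5% power. The gain is 2/0.53 − 2 = 1.77 months. Both stated figures reproduce.

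**2. Chance imbalance.** For a factor of prevalence p, the SD of the between-arm difference is √[p(1 − p)(1/33 + 1/66)]:

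- p = 15%: 7.6 points
- p = 20%: 8.5 points
- p = 30%: 9.8 points, so a difference of 10 points or more has probability about 31%

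**3. Effect of adjustment on power for PFS.** The documents give no prognostic hazard ratios or prevalences, so these are assumptions: ECOG 0/1/2 in 30/50/20%; Stage II/III/IV in 10/70/20%; the three regimens in 20/50/30%; immunotherapy in 40% with HR 0.7. Each scenario has 1,500 simulated trials of 99 patients, 1:2 permuted blocks within the six cells, exponential PFS with a 2-month placebo median and censoring at 8 months (78 to 82 events). The treatment HR is 0.53 conditional on the covariates. The Cox model is stratified by the six cells, with ECOG and stage entered as three-level scores.

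| HR per level (ECOG, stage) | Planned log-rank | Log-rank, 54 cells | Adjusted Cox | Cox minus planned |
|---|---|---|---|---|
| 1, 1 | 76.6% | 52.0% | 76.3% | −0.3 |
| 1.25, 1.25 | 75.5% | 51.5% | 76.5% | +1.0 |
| 1.5, 1.5 | 71.3% | 51.2% | 75.7% | +4.4 |
| 2, 1.5 | 64.9% | 51.1% | 73.6% | +8.7 |
| 2, 2 | 61.1% | 51.4% | 72.3% | +11.2 |

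The first row is below 80% because 8-month censoring yields about 82 events; Schoenfeld power at 80 events is 76.3%. The simulation error of one power figure is about √(0.75 × 0.25/1500) = 1.1 points, so the first two rows amount to no loss and little gain. At a treatment HR of 1, rejection was 4.4-5.5% for the planned test and 4.9-5.7% for the Cox model.

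**4. Why not more strata.** Adding three ECOG levels and three stage levels gives 6 × 3 × 3 = 54 cells for 99 patients. Most are too sparse to compare the arms within, which explains the 51-52% column.

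**5. Sensitivity to coding.** Step 3 used three-level scores. Rerunning it with two-level covariates (ECOG 2 v 0-1, Stage IV v II/III) gave 76.4, 75.4, 72.7, 69.1 and 68.3% in the same row order: smaller gains (about 0, 1, 4 and 7 points in the last four rows) when the true effect is graded. In a separate run, excess risk was confined to ECOG 2 and Stage IV, with six strata, an 8-month placebo median and 30 months of follow-up. It gave 71.4% v 74.9% (ECOG HR 2 in 15%, stage HR 1.5 in 20%) and 64.2% v 74.1% (HR 3 in 25%, HR 2 in 30%), which is 3.5 and 9.9 points. The mean estimated HR was 0.54-0.57 unadjusted and 0.52 adjusted.

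**The case against.** The case for leaving Section 13.7 alone is respectable. A log-rank test stratified by the randomisation factors is standard and assumption-light. Its type I error is correct, and chance imbalance is already allowed for in its p-value. Section 13.4 tabulates baseline characteristics by arm, so an imbalance would be seen. The endpoints are secondary, and the comparison is only something the plan may do. A Cox model also leans on proportional hazards, although study drug stops after six cycles and follow-up continues to 2.5 years. All of this stands. It limits the severity and argues for keeping the log-rank test, but it does not argue against a pre-specified adjusted estimate beside it.

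Three stronger readings are tempting, and the documents do not support them.

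- A reader might infer that the strata are purely pneumonitis factors. Section 2 says durvalumab prolonged both PFS and OS, so immunotherapy exposure is a survival factor on the plan's own account.
- A reader might infer that ECOG and stage dominate survival here. Section 1.4.2 supports only ECOG, only for OS, and in advanced or recurrent disease; it gives no all-patient PFS to set against 11.6 weeks. No prognostic figure for stage appears anywhere.
- A reader might infer that the stated 80% power is wrong. It reproduces for the plan's own quantity. The simulated shortfall arises partly because 0.53 was set as the covariate-conditional hazard ratio, which differs by definition from the marginal one that an unadjusted test addresses.

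**Conclusion.** The concern holds as a minor, inexpensive improvement. The planned test is valid but leaves unused a baseline variable that the trial records and that its background shows to be prognostic for OS, and it also leaves stage unused. The gain in power from adjustment is about 0 to 1 points if prognostic effects are weak, about 4 points at HR 1.5 per level, and about 9 to 11 points if ECOG has HR 2 per level. Two-level coding recovers less if effects are graded. When the factors are inert, nothing material is lost. Adjustment also takes chance imbalance in these factors out of the reported hazard ratio.

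The sizes rest on assumed effects, prevalences and exponential PFS. No corresponding calculation was made for OS, so only the direction should be carried over to it.

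**What to change.** In Section 13.7, pre-specify for PFS and OS a Cox model stratified by the randomisation factors (chemotherapy regimen and immunotherapy exposure), with baseline ECOG (2 v 0-1) and stage (oligometastatic IV v II/III) as covariates. Report its adjusted hazard ratio alongside the stratified log-rank test. Fix the coding before unblinding; if a graded ECOG effect is expected, entering 0/1/2 keeps more of the gain. State that ECOG and stage will not be added as log-rank strata.

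Name the log-rank strata in Section 13.7 as well, because Section 13.5 lists chemotherapy regimen alone while Sections 13.1 and 13.2 add immunotherapy.

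The cost is a few sentences and one case report form field: stage, taken from the eligibility work-up, since the eligibility form asks only whether the patient falls within Stage II to IV. No extra patients or visits are needed. The price in interpretation is that the adjusted hazard ratio is a conditional one and relies on proportional hazards, which should be checked and reported.

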3.2 Secondary Objectives

- To compare the quality of life (QOL) in patients who received nintedanib versus placebo during active treatment until 6 months after completion of treatment.
- To compare the progression-free survival, overall survival and 1-year progression-free survival rate in patients who received nintedanib versus placebo.
- To compare pulmonary function test (PFT) results and RP score in patients who received nintedanib versus placebo.
- To compare the composite index (based on PFT, RP score and QOL) at the end of active treatment and 6 months after completion of treatment between patients who received nintedanib versus placebo.

3.3 Exploratory Objective:

- To investigate blood-based biomarkers in evaluating risk of developing radiation pneumonitis as well as the efficacy of nintedanib.

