13.1 Sample Size Determination

A maximum of 18 participants will be enrolled to the non-randomized dose escalation portion of this study. The number of participants required is a function of the unknown dose-toxicity relationship.

A maximum of 99 participants will be enrolled to the randomized Phase 2 portion of this study (excluding patients replaced due to ineligibility or inability to start therapy). Participants will be randomized in a 1:2 fashion, stratified by chemotherapy regimen (i.e., platinum with etoposide, platinum with taxane, platinum with pemetrexed) and immune therapy (i.e. durvalumab), into the placebo and nintedanib arms. Accrual is expected to take 4 years.

Evaluable patients will be any patient who receives at least one dose of study drug.

The sample size justification is based on the primary analysis: a comparison of the rate of radiation pneumonitis at 6 months after completion of chemoradiation between the placebo and nintedanib arms, stratified by chemotherapy regimen (i.e., platinum with etoposide, platinum with taxane, platinum with pemetrexed) and immune therapy exposure (i.e. durvalumab), using the one-sided Cochran-Mantel-Haenszel (CMH) exact test at a significance level of 0.05. The expected rate of Grade 2 or higher radiation pneumonitis is 30% in the placebo arm, and a decrease in this rate to 10% in the nintedanib arm would be considered clinically significant; which is equivalent to a common odds ratio (COR) of approximately 0.26.

Using a simulation based on the proposed study design; if there is no improvement in the rate of radiation pneumonitis (COR = 1.0), then there is a 59.0% chance of stopping early for futility. If the true COR is 0.26, then there is only a 10.6% chance of stopping early for futility. If the true common odds ratio is 0.26, then there is an 80.1% chance of detecting a significant reduction in the rate of Grade 2 or higher radiation pneumonitis in the nintedanib arm. If the COR is 1.0, then the chance of detecting a significant reduction is 4.2%; which can be considered the effective type-I error rate.

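### Section 13.7 tests QOL changes with unstratified two-sample tests, although 13.2 requires stratified tests, and specifies no analysis over the period that the QOL objective names

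*Combined protocol and SAP*

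**What the plan says.** Section 3.2 sets the objective: "To compare the quality of life (QOL) in patients who received nintedanib versus placebo during active treatment until 6 months after completion of treatment". It names no time point or summary measure.

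Section 13.7 first describes reporting: "The overall and sub-category QOL and symptom scores (ranging from 0 to 68) will be reported by study arm and time". It then turns to testing: "Changes in the QOL and symptom scores may be compared between study arms using the Wilcoxon rank sum or independent sample t-tests, as appropriate". On multiplicity it adds: "No adjustments for multiple testing will be made as this is a secondary analysis". Secondary analyses are run "at a significance level of 0.05". No QOL missing-data rule is given.

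Section 13.2 gives a general rule: "The randomization and the significance tests applied in the analyses will be stratified by chemotherapy regimen", and by exposure to immunotherapy agents. It is not limited to the primary analysis.

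Within 13.7, OS and PFS get a stratified log-rank test and response rates a Cochran-Mantel-Haenszel exact test. QOL, PFT and RP scores get two-sample tests with no mention of strata.

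**The concern.** Two things do not fit together.

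- **Stratification.** The rule in 13.2 covers the significance tests in general. The Wilcoxon rank sum and independent-sample t-tests, as named, take no account of strata.
- **Objective and analysis.** The objective covers a period, but both tests take one value per patient. Nothing says whether that value is the change at one visit, at each visit in turn, or a summary. Nor is it said which score is the main one, or which of the two tests applies.

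At stake is whether QOL gets one interpretable answer. If the comparison is repeated over visits and scores, some nominally significant result is fairly probable by chance. If one visit is used, information from the other four is lost.

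**Working it through.** **Inputs from the documents**

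- Arms: "With a sample size of $n = 33$ in the control and $n = 66$ in the treatment group" (Section 13.7).
- Scheduled post-baseline QOL visits in the objective's window (Sections 9.4 and 9.6-9.8): Cycle 3, Cycle 6, end of active treatment, 76-97 days and 166-187 days after the last dose. That is 5. Baseline is Cycle 1 Day 1.
- Scores (Appendix F): DRS-P, DRS-E, TSE and FWB plus the overall score. That is 5. The 17 items scored 0-4 give a maximum of 17 × 4 = 68, matching 13.7.
- Possible comparisons: 5 × 5 = 25.

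**Assumptions not in the documents:** equal correlation r between visits (0.4-0.7), complete data, a constant effect, two-sided 0.05 (13.7 does not state sidedness for QOL).

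**The plan's own figure.** Section 13.7 states 80% power for 0.5 SD. The standard error factor is √(1/33 + 1/66) = 0.2132. If 0.5 SD refers to the SD of the value tested, 0.5/0.2132 = 2.345, giving 65% power (normal) or 64% (t-test). One-sided it is about 76% or 75%. So 80% is not reproduced on that reading. It is reached two-sided if 0.5 SD refers to the SD of the score and r is about 0.65: the variance of change is 2(1 − 0.65) = 0.70, and 0.5/(√0.70 × 0.2132) = 2.80. The documents do not state such a correlation.

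**Chance findings with no true effect.** If visits are equally correlated, changes sharing one baseline have covariance 1 − r and variance 2(1 − r), so they correlate at 0.5 whatever r is. With that 0.5 between visits and an assumed correlation between scores, simulation of 25 tests gives:

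| Between-score correlation | Any p < 0.05, either direction | Any p < 0.05 favouring nintedanib |
|---|---|---|
| 0.3 | 60% | 33% |
| 0.5 | 55% | 28-29% |
| 0.7 | 46% | 23-24% |
| Overall score only, 5 visits | 18% | 9% |

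For reference, 25 independent tests would give 1 − 0.95^25 = 72%.

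**Power for a constant 0.5 SD effect.** Variances in units of the score variance:

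- single-visit change: 2(1 − r)
- single-visit ANCOVA on baseline: 1 − r²
- baseline-adjusted mean of five visits: (1 + 4r)/5 − r²

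At r = 0.5 these are 1.00, 0.75 and 0.35. The ratios 0.5/(SD × 0.2132) are 2.345, 2.708 and 3.964. Power from the t distribution:

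| r | Change | ANCOVA, one visit | Adjusted five-visit mean |
|---|---|---|---|
| 0.4 | 56% | 72% | 97% |
| 0.5 | 64% | 76% | 98% |
| 0.6 | 74% | 83% | 98% |
| 0.7 | 85% | 90% | 99% |

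At r = 0.5, baseline adjustment adds 12 points and averaging a further 22 (76% to 98%, before rounding 76.4% to 97.5%, so 21).

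**The case against.** **Twenty-five tests are not prescribed.** A reader might infer from 13.7 that each score is tested at each visit. The phrase about arm and time governs the descriptive statistics, and the comparison sentence is permissive. Visit-by-visit testing is the natural reading of a one-value-per-patient test, but 25 is a ceiling. This stands.

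**A false QOL benefit is not likely.** The 46-60% counts chance findings of harm as well as benefit. In favour of nintedanib it is 23-33%, or 9% if only the overall score is tested. The score correlations may also be too low, because the overall score contains the sub-scores. With ten of 17 items under DRS-P as the table was extracted, that pair correlates at least √(10/17) = 0.77 if items have equal variance and non-negative correlation. Building the overall score as the item sum, with assumed inter-item correlation 0.2-0.5, gives about 40-51% in either direction and 20-27% favouring nintedanib. This stands.

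**Multiplicity is openly waived.** For a Phase II secondary endpoint that is a disclosed choice. It does not settle which result answers the objective, or the conflict with 13.2.

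**13.2 and 13.7 might be read together.** Stratified rank tests exist, so 13.2 could be taken to modify the named tests. But 13.7 writes the stratified form for OS and PFS and omits it for QOL, PFT and RP scores. The text needs reconciling either way.

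**Missing data.** A reader might infer that patients missing a visit are dropped. The plan states no rule, so this cannot be attributed to it.

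**Averaging has costs.** Section 1.6 lists gastrointestinal effects and fatigue as drug risks, so QOL could move in opposite directions on and off treatment. The composite-index objective names end of treatment and 6 months after, so interest in specific times is legitimate. This stands and shapes the fix.

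**Conclusion.** The concern holds in a limited form. The QOL tests named in 13.7 are unstratified, against the general rule in 13.2, and no analysis over the objective's period is specified. These two points rest on the text alone.

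The sizes rest on assumptions. The probability of at least one nominally significant result among up to 25 comparisons is about 46-60% in either direction and 23-33% in favour of nintedanib, given between-visit correlation 0.5 for changes and between-score correlation 0.3-0.7. The power advantage of a five-visit adjusted average (97-99%, against 72-90% for single-visit ANCOVA and 56-85% for unadjusted change) assumes complete data, a constant effect and equal visit correlation of 0.4-0.7. Part of the gap to the unadjusted test is due to baseline adjustment, so averaging should not be credited with all of it. Dropout or an effect that varies over time would shrink these figures.

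The documents do not support saying that a false QOL benefit is likely, that the plan commits to 25 tests, or that the period objective can never be tested. They support saying that no test over the period is specified. The change is worth making, but it concerns a secondary objective and leaves the primary analysis untouched.

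**What to change.** In Section 13.7, specify one repeated-measures model for the overall QOL score:

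- outcome at the five scheduled post-baseline visits in the objective's window;
- terms for arm, visit, arm-by-visit, baseline score, chemotherapy regimen and immunotherapy stratum;
- the arm difference averaged over the visits as the single QOL test, two-sided 0.05;
- visit-level results (including end of treatment and 6 months after) and sub-category results as estimates with confidence intervals;
- questionnaires taken because pneumonitis was suspected left out, since their timing depends on the event that treatment is meant to prevent.

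State in 13.2 or 13.7 whether the PFT and RP score tests, which use the same unstratified wording, are also to be stratified.

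The cost is SAP wording and standard software; no new data or patients are needed. Three downsides should be written into the plan:

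- An average can hide opposing on- and off-treatment effects, which is why the visit-level estimates must be shown.
- End-of-treatment and later visits are timed from stopping or the last dose, so early stoppers are assessed at different times since randomization.
- Death and dropout need a stated approach. After six 28-day cycles (168 days), the last visit falls at about day 168 + 166 = 334 to 168 + 187 = 355, while 13.7 posits a placebo median PFS of about 2 months. One option is a while-alive interpretation with a sensitivity analysis.

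Visit-level and sub-category p-values would no longer support claims.
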